### 8.1.2 Relationship Categorization

A physician/investigator must make the assessment of relationship to investigational product for each AE. The investigator should decide whether, in his or her medical judgment, there is a reasonable possibility that the event may have been caused by the investigational product. If there is no valid reason for suggesting a relationship, then the AE should be classified as “not related”. Otherwise, if there is any valid reason, even if undetermined or untested, for suspecting a possible cause-and-effect relationship between the investigational product and the occurrence of the AE, then the AE should be considered “related”. The causality assessment must be documented in the source document.

The following additional guidance may be helpful:

Term	Relationship Definition
Related	The temporal relationship between the event and the administration of the investigational product is compelling and/or follows a known or suspected response pattern to that product, and the event cannot be explained by the subject’s medical condition, other therapies, or accident.
Not Related	The event can be readily explained by other factors such as the subject’s underlying medical condition, concomitant therapy, or accident and no plausible temporal or biologic relationship exists between the investigational product and the event.

### 8.1.3 Outcome Categorization

The outcome of AEs must be recorded during the course of the study on the CRF. Outcomes are as follows:

- Fatal
- Not Recovered/Not Resolved
- Recovered/Resolved
- Recovered/Resolved With Sequelae
- Recovering/Resolving
- Unknown

### 8.1.4 Clinical Laboratory and Other Safety Evaluations

A change in the value of a clinical laboratory, vital sign, or ECG assessment can represent an AE if the change is clinically relevant or if, during treatment with the investigational product, a shift of a parameter is observed from a normal value to an abnormal value, or a further worsening of an already abnormal value. When evaluating such changes, the extent of deviation from the reference range, the duration until return to the reference range, either while continuing treatment or after the end of treatment with the investigational product, and the range of variation of the respective parameter within its reference range, must be taken into consideration.

If, at the end of the treatment phase, there are abnormal clinical laboratory, vital sign, or ECG values which were not present at the pretreatment value observed closest to the start of study treatment, further investigations should be performed until the values return to within the reference range or until a plausible explanation (eg, concomitant disease) is found for the abnormal values.

The investigator should decide, based on the above criteria and the clinical condition of a subject, whether a change in a clinical laboratory, vital sign, or ECG parameter is clinically significant and therefore represents an AE.

### **8.1.5 Pregnancy**

All pregnancies are to be reported from the time informed consent is signed until the defined follow-up period stated in Section 7.1.3.

Any report of pregnancy for any female study participant must be reported within 24 hours to the Shire Global Safety Department using the Shire Investigational and Marketed Products Pregnancy Report Form. A copy of the Shire Investigational and Marketed Products Pregnancy Report Form (and any applicable follow-up reports) must also be sent to the CRO/Shire medical monitor using the details specified in the [emergency contact information](#) section of the protocol. The pregnant female study participant must be withdrawn from the study.

Every effort should be made to gather information regarding the pregnancy outcome and condition of the infant. It is the responsibility of the investigator to obtain this information within 30 calendar days after the initial notification and approximately 30 calendar days post partum.

Pregnancy complications such as spontaneous abortion/miscarriage or congenital abnormality are considered SAEs and must be reported using the Shire Clinical Study Serious Adverse Event and Non-serious AEs Required by the Protocol Form. Note: An elective abortion is not considered an SAE.

In addition to the above, if the investigator determines that the pregnancy meets serious criteria, it must be reported as an SAE using the Shire Clinical Study Serious Adverse Event and Non-serious AEs Required by the Protocol Form as well as the Shire Investigational and Marketed Products Pregnancy Report Form. The test date of the first positive serum/urine  $\beta$ -hCG test or ultrasound result will determine the pregnancy onset date.

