### 3.1.4 Follow-up

[figure not shown]
A follow up telephone call (or in-person follow-up contact at the investigator's discretion) will take place 7± 2 days following the subject's last dose of investigational product to collect information on any ongoing or new adverse events (AEs), serious adverse events (SAEs) or concomitant medications, as appropriate.

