### 3.2 Duration and Study Completion Definition

The subject's maximum duration of participation is expected to be approximately 46 days if the maximum screening, treatment and follow-up durations are used.

- Maximum planned duration of the screening period: 28 days
- Planned duration for the treatment period: 9 days
- Planned duration for the follow up: 7±2 days

The study will be completed in approximately 3 months.

The Study Completion Date is defined as the date the final subject, across all sites, completes their final protocol-defined assessment. Please note that this includes the follow-up visit or contact, whichever is later. The Study Completion Date is used to ascertain timing for study results posting and reporting.

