### 4.4 Reproductive Potential

#### 4.4.1 Female Contraception

Sexually active females of childbearing potential should be using an acceptable form of contraception. Females of childbearing potential must be advised to use acceptable contraceptives throughout the study period and for 30 days following the last dose of investigational product. Females of childbearing potential who are not currently sexually active must agree to use acceptable contraception, as defined below, if they become sexually active during the period of the study and 30 days following the last dose of investigational product.

Female subjects should be either:

- Postmenopausal (12 consecutive months of spontaneous amenorrhea and  $\geq$  age 51 years)

- Surgically sterile (having undergone one of the following surgical acts: hysterectomy, bilateral tubal ligation, bilateral oophorectomy or bilateral salpingectomy) and at least 6 weeks post-sterilization, or
- Females of childbearing potential with a negative urine and/or serum  $\beta$ -hCG pregnancy test at screening and at Day -1. Females of childbearing potential must agree to abstain from sexual activity that could result in pregnancy or agree to use acceptable methods of contraception.

Acceptable methods of contraception are:

- Intrauterine devices plus condoms
- Double-barrier methods (eg, condoms and diaphragms with spermicidal gel or foam)

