#### **6.2.2 Dosing**

After satisfying all screening and entry criteria, anagrelide and/or omeprazole will be administered to all subjects according to the following schedule:

Day 1: Anagrelide 1 mg, (administered orally as two 0.5 mg capsules) will be administered to all subjects at approximately 8:00 in the morning on Day 1. Subjects are required to fast for 10 hours prior to and until 4 hours following administration of anagrelide on Day 1.

Days 2-7: Omeprazole 40 mg (administered orally, QD) will be administered to all subjects on Days 2-7. Omeprazole will be administered at approximately 8:00 in the morning, prior to breakfast.

Day 8: Anagrelide 1 mg and omeprazole 40 mg will be administered concurrently to all subjects at approximately 8:00 in the morning on Day 8. Subjects are required to fast for 10 hours prior to and until 4 hours following administration of anagrelide and omeprazole on Day 8.

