### 7.1.3 Follow-up

A follow up telephone call (or in-person follow-up contact at the investigator's discretion) will take place  $7 \pm 2$  days following the subject's last dose of investigational product to collect information on any ongoing or new AEs, SAEs or concomitant medications, as appropriate. All AEs and SAEs that are not resolved at the time of this contact will be followed to closure (see Section [8.1](#)).

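### Pregnancy reporting is stated to end 5–9 days after the last dose, while contraception is required for 30 days, so 21–25 days are left unsought and the duty to report late is unclear

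*Protocol*

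**What the plan says.** Section 8.1.5 of the protocol opens with the reporting window: "All pregnancies are to be reported from the time informed consent is signed until the defined follow-up period stated in Section 7.1.3". Section 7.1.3, to which it refers, provides one telephone or in-person contact 7±2 "days following the subject's last dose of investigational product to collect information on any ongoing or new AEs, SAEs or concomitant medications, as appropriate". Pregnancy is not among the topics listed for that contact. Section 3.2 gives the same length: "Planned duration for the follow up: 7±2 days". Section 7.1.4 plans no aftercare.

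Section 4.4.1 sets a longer period for contraception. Women of childbearing potential must be advised to "use acceptable contraceptives throughout the study period and for 30 days following the last dose of investigational product". Those not currently sexually active must agree to contraception "if they become sexually active during the period of the study and 30 days following the last dose of investigational product".

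Two other provisions bear on late reports. Later in Section 8.1.5, any report of pregnancy in a female participant has to reach the sponsor's safety department within 24 hours; that sentence gives no end date. Section 8.2.4 requires SAEs discovered after the study has completed to be reported, but only if they are considered related to investigational product.

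**The concern.** The protocol asks women to avoid pregnancy for 30 days after dosing but states a reporting window that closes after 5–9 of those days. No contact is planned after that, and no provision asks a woman to tell the site if she becomes pregnant later in the contraception period.

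What is at stake is safety information. Section 8.1.5 wants the outcome of each pregnancy and the condition of the infant followed up, and that process starts with a notification. For a pregnancy recognised in week 3 or 4 after the last dose, no notification is solicited, and a site reading the first sentence of 8.1.5 literally could treat the case as out of scope. Safety and tolerability are the study's secondary objective.

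**Working it through.** This is day counting plus a reading of the reporting rules. No sample-size or power formula is involved.

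**Inputs**
- Last dose: Section 6.2.2, "Day 8: Anagrelide 1 mg and omeprazole 40 mg will be administered concurrently to all subjects at approximately 8:00 in the morning on Day 8". For a subject who completes dosing, the last dose of both products is on Day 8.
- Follow-up contact: 7±2 days after the last dose (Section 7.1.3), so 7 − 2 = 5 to 7 + 2 = 9 days.
- Contraception period: 30 days after the last dose (Section 4.4.1).
- Discharge: Day 9 (Section 7.1.2.2).

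**The plan's own figure.** Section 3.2 gives a maximum participation of about 46 days: 28 (screening) + 9 (treatment) + 9 (follow-up) = 46. This reproduces, and confirms that the protocol counts follow-up as at most 9 days. Counting follow-up from Day 8 instead gives 28 + 8 + 9 = 45 days; the one-day difference does not matter here.

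**Coverage.** With contact *f* days after the last dose, the uncovered share is (30 − *f*)/30. The contraception period ends on Day 8 + 30 = Day 38.

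| Contact, days after last dose | Study day of contact | Days not covered | Share of 30 days |
|---|---|---|---|
| 5 | 8 + 5 = 13 | 30 − 5 = 25 | 83.3% |
| 7 | 8 + 7 = 15 | 30 − 7 = 23 | 76.7% |
| 9 | 8 + 9 = 17 | 30 − 9 = 21 | 70.0% |

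Most of the contraception period lies outside the stated window wherever the contact falls within ±2 days.

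**Which conceptions are affected.** Subjects are confined from Day −1 until Day 9. The contact falls on Day 13–17, which is 13 − 9 = 4 to 17 − 9 = 8 days after discharge. Assuming that a pregnancy is not usually recognised within about a week of conception (the documents give no figure), few conceptions after discharge could be known at the contact.

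Conceptions before admission are different. Section 7.2.2.6 requires a serum test in all females at the scheduled visits, when pregnancy is suspected and on withdrawal. The schedule in SAP Appendix 15.1 shows tests at screening and Day −1, with further marks late in the schedule whose columns cannot be read reliably in the text version available here. Those tests may find such pregnancies.

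**Does another rule close the gap?**
- The 24-hour rule in 8.1.5 says how fast a report is passed on. It creates no occasion on which a pregnancy would be sought, and it follows the sentence that sets the end of the window.
- Section 8.2.4 reaches past the end of the study only for related SAEs. Under 8.1.5 a pregnancy is an SAE only if it meets serious criteria or has complications such as miscarriage or congenital abnormality.

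Neither rule provides for collecting pregnancies between the contact and Day 38.

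**The case against.** The strongest reply is that contraception and reporting periods serve different purposes and may differ without contradiction. Section 4.4.1 sets a precaution and creates no reporting duty. That is correct. A reader might infer that the protocol names a 30-day risk period and then fails to monitor it. The documents do not support this, because they call the 30 days a contraception requirement and nothing more. What stands is that the reporting window is much shorter than the period in which the protocol wants pregnancy avoided, and no reason is given.

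A reader might also infer that nothing requires a late pregnancy to be reported. That goes too far. The 24-hour sentence in 8.1.5 has no end date of its own, the outcome follow-up after it runs to about 30 days post partum, and a later complication judged related would come under 8.2.4. A late report is therefore ambiguous, not clearly excluded.

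A third inference would be that the missed cases are drug-exposed pregnancies. The documents give no figure showing that a conception on, say, day 15 after the last dose is exposed to either drug or its effect. Anagrelide sampling stops at 12 hours and omeprazole sampling at 24 hours.

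Finally, the 70–83% is a share of calendar days, not of risk or of expected pregnancies. About 20 subjects of both sexes are planned, and the number of women of childbearing potential is not stated, so no expected count of missed cases can be derived. All of this limits the weight of the point. It does not remove the mismatch between 8.1.5 and 4.4.1.

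**Conclusion.** The mismatch is real and modest in consequence. The stated reporting window covers 5–9 of the 30 days of required contraception and leaves 21–25 days (70–83%) in which pregnancies are not sought and the duty to report them is ambiguous. The gap mainly concerns conceptions after discharge.

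The day counts assume that the last dose is given on Day 8 and that the reference in 8.1.5 to the Section 7.1.3 follow-up means the window closes at that contact. The restriction to conceptions after discharge rests on confinement to Day 9 and on the scheduled serum tests.

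The point bears on the completeness of safety data. It does not touch the primary pharmacokinetic analysis or the sample size.

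**What to change.** Reconcile Section 8.1.5 with Section 4.4.1. State in 8.1.5 that pregnancies are reported from informed consent until the end of the contraception period already set in 4.4.1, which is Day 38 for a subject whose last dose is on Day 8. That moves the end of the window by 38 − 17 = 21 to 38 − 13 = 25 days, leaves none of the 30 days uncovered, and removes the doubt about the undated 24-hour sentence.

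Have the site ask women of childbearing potential, at discharge and again at the follow-up call, to notify it of any pregnancy in that period.

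The cost is one sentence in 8.1.5 and one line each in the discharge instructions and the call script. The downside is that pregnancy reporting stays open about three weeks longer for these women. No visit or test is added, and the contraception rule is unchanged.

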### **8.1.6 Abuse, Misuse, Overdose, and Medication Error**

Abuse, misuse, overdose, or medication error (as defined below) must be reported to the sponsor according to the SAE reporting procedure whether or not they result in an AE/SAE as described in Section 8.2. Note: The 24-hour reporting requirement for SAEs does not apply to reports of abuse, misuse, overdose, or medication errors unless these result in an SAE.

The categories below are not mutually exclusive; the event can meet more than 1 category.

- **Abuse** – Persistent or sporadic intentional intake of investigational product when used for a non-medical purpose (eg, to alter one’s state of consciousness or get high) in a manner that may be detrimental to the individual and/or society
- **Misuse** – Intentional use of investigational product other than as directed or indicated at any dose (Note: this includes a situation where the investigational product is not used as directed at the dose prescribed by the protocol)
- **Overdose** – Intentional or unintentional intake of a dose of investigational product higher than the protocol-prescribed dose
- **Medication Error** – An error made in prescribing, dispensing, administration, and/or use of an investigational product. For studies, medication errors are reportable to the sponsor only as defined below.

Medication errors should be collected/reported for all products under investigation.

The administration and/or use of an expired investigational product should be considered as a reportable medication error.

## 8.2 Serious Adverse Event Procedures

### 8.2.1 Reference Safety Information

The reference for safety information for this study is the investigator’s brochure which the sponsor has provided under separate cover to all investigators.

The reference for safety information for omeprazole (PRILOSEC®) is the FDA-approved package insert which the sponsor has provided under separate cover to all investigators

### 8.2.2 Reporting Procedures

All initial and follow-up SAE reports must be reported by the investigator to the Shire Global Safety Department and the CRO/Shire medical monitor within 24 hours of the first awareness of the event. Note: The 24-hour reporting requirement for SAEs does not apply to reports of abuse, misuse, overdose, or medication errors (see Section 8.1.6) unless they result in an SAE.

The investigator must complete, sign, and date the Shire Clinical Study Serious Adverse Event and Non-serious AEs Required by the Protocol Form and verify the accuracy of the information recorded on the form with the corresponding source documents (Note: Source documents are not to be sent unless requested) and fax or e-mail the form to the Shire Global Safety Department. A copy of the Shire Clinical Study Serious Adverse Event and Non-serious AEs Required by the Protocol Form (and any applicable follow-up reports) must also be sent to the CRO/Shire medical monitor using the details specified in the [emergency contact information](#) section of the protocol.

### 8.2.3 Serious Adverse Event Definition

A *serious adverse event* (SAE) is any untoward medical occurrence (whether considered to be related to investigational product or not) that at any dose:

- Results in death
- Is life-threatening. Note: The term “life-threatening” in the definition of “serious” refers to an event in which the subject was at risk of death at the time of the event; it does not refer to an event which hypothetically might have caused death if it was more severe.
- Requires inpatient hospitalization or prolongation of existing hospitalization. Note: Hospitalizations that are the result of elective or previously scheduled surgery for pre-existing conditions and have not worsened after initiation of treatment should not be classified as SAEs. For example, an admission for a previously scheduled ventral hernia repair would not be classified as an SAE; however, complication(s) resulting from a hospitalization for an elective or previously scheduled surgery that meet(s) serious criteria must be reported as SAE(s).
- Results in persistent or significant disability/incapacity
- Is a congenital abnormality/birth defect
- Is an important medical event. Note: Important medical events that may not result in death, be life-threatening, or require hospitalization may be considered an SAE when, based upon appropriate medical judgment, they may jeopardize the subject and may require medical or surgical intervention to prevent 1 of the outcomes listed in this definition. Examples of such medical events include allergic bronchospasm requiring intensive treatment in an emergency room or at home; blood dyscrasias or convulsions that do not result in inpatient hospitalization; or the development of drug dependency or drug abuse.

### 8.2.4 Serious Adverse Event Collection Time Frame

All SAEs (regardless of relationship to study) are collected from the time the subject signs the informed consent until the defined follow-up period stated in Section 7.1.3 and must be reported to the Shire Global Safety Department and the CRO/Shire medical monitor within 24 hours of the first awareness of the event.

In addition, any SAE(s) considered “related” to the investigational product and discovered by the investigator at any interval after the study has completed must be reported to the Shire Global Safety Department within 24 hours of the first awareness of the event.

### 8.2.5 Serious Adverse Event Onset and Resolution Dates

The onset date of the SAE is defined as the date the event meets serious criteria. The resolution date is the date the event no longer meets serious criteria, the date the symptoms resolve, or the event is considered chronic. In the case of hospitalizations, the hospital admission and discharge dates are considered the onset and resolution dates, respectively.

In addition, any signs or symptoms experienced by the subject after signing the informed consent form, or leading up to the onset date of the SAE, or following the resolution date of the SAE, must be recorded as an AE, if appropriate.

### **8.2.6 Fatal Outcome**

Any SAE that results in the subject's death (ie, the SAE was noted as the primary cause of death) must have fatal checked as an outcome with the date of death recorded as the resolution date. For all other events ongoing at the time of death that did not contribute to the subject's death, the outcome should be considered not resolved, without a resolution date recorded.

For any SAE that results in the subject's death or any ongoing events at the time of death, unless another investigational product action was previously taken (eg, drug interrupted, reduced, withdrawn), the action taken with the investigational product should be recorded as "dose not changed" or "not applicable" (if the subject never received investigational product). The investigational product action of withdrawn should not be selected solely as a result of the subject's death.

### **8.2.7 Regulatory Agency, Institutional Review Board, Ethics Committee, and Site Reporting**

The sponsor is responsible for notifying the relevant regulatory authorities of related, unexpected SAEs.

In addition the sponsor is responsible for notifying active sites of all related, unexpected SAEs occurring during all interventional studies across the anagrelide program.

The investigator is responsible for notifying the local IRB, local EC, or the relevant local regulatory authority of all SAEs that occur at his or her site as required.

